## **1.2. Lay Summary**

Birt-Hogg-Dubé syndrome (BHD) is an uncommon genetic disease characterized by tumors in the hair follicles and kidneys, as well as lung cyst formation. These lung cysts can rupture thus placing patients with BHD at a higher risk for development of pneumothoraces, or collapsed lungs.

Pulmonary Langerhans cell histiocytosis (PLCH) is an uncommon disease characterized by the formation of cysts in the lungs, and is strongly associated with smoking cigarettes. Similar to BHD, patients with PLCH have an increased risk of development of pneumothoraces.

The safety of air travel in patients with BHD and PLCH is not established. The concern with air travel in these diseases is related to the risk of cyst expansion with decreasing atmospheric pressure, which could lead to cyst rupture causing a pneumothorax. Safety of air travel has been studied for patients with lymphangioleiomyomatosis (LAM), another rare cystic lung disease. Based on the results from studies done in patients with LAM, recommendations regarding air travel are provided to patients with BHD and PLCH. The aim of this study is to conduct a survey-based assessment of patients with BHD and PLCH and establish the risk of pneumothorax associated with air travel in these diseases.

As a follow up to the original protocol, we plan to re-contact all patients who gave us permission in the survey to contact them again. We will obtain results of their lung function tests and images of CT chest to correlate PFT data and cyst preponderance (size, number, volume etc.) with the risk for spontaneous pneumothorax.

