### **2.2. Objectives**

1. To define the risk of pneumothorax related to air travel in patients with BHD and PLCH.
2. To establish a contact registry for patients with BHD and PLCH, in order to facilitate participation in future trials.
3. To describe the demographic and clinical characteristics of patients with BHD and PLCH, as well as ascertain clinical practices related to management and surveillance of related medical conditions, such as surveillance of renal tumors in patients with BHD.
4. To determine the relationship between lung function, and radiographic cyst characteristics and the risk of spontaneous pneumothorax in patients with BHD and PLCH.

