### **3.0 Background**

BHD is a rare, autosomal dominantly inherited genodermatosis characterized by the formation of hair follicle tumors, kidney tumors, and pulmonary cysts. Pulmonary cysts are seen in 80-100% of patients with BHD, and lead to an increased risk of development of pneumothorax in these patients. Zbar et al., have reported that the risk of development of pneumothorax is 32-fold higher in patients with BHD as compared to the general population.

Atmospheric pressure changes have the potential to cause cyst expansion leading to an increased chance of cyst rupture causing a pneumothorax. Based on this risk, patients with BHD are advised to not undertake scuba diving, although no disease specific data exists for this recommendation. In general, air travel is considered to be safe in patients with diffuse cystic lung diseases, although disease specific data for safety of air travel in BHD are lacking.

PLCH is a rare diffuse cystic lung disease seen most commonly in young-middle aged adults, and is associated with exposure to cigarette smoke in greater than 90% of patients.

Approximately 15% of patients with PLCH develop a pneumothorax over their lifetime, with a recurrence rate of approximately 60% after a sentinel event. Similar to BHD, recommendations regarding air travel are given to patients with PLCH on the basis of extrapolation from other diseases.

Having specific information about safety of air travel in BHD and PLCH will help these patients make informed decisions about air travel. We aim to conduct a questionnaire-based assessment of patients with BHD and PLCH to ascertain the risk of pneumothorax related to air travel. In the first part of this study we will distribute the questionnaires for BHD, followed later by the PLCH survey. In addition, we aim to establish a contact registry for these patients in order to answer future clinical questions.

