With the current amendment, we will re-contact patients with BHD and PLCH, who gave us the permission to contact them in future for other projects. We will ask permission to obtain their medical records, specifically their pulmonary function tests (PFTs), and CT scan(s) of the chest. We will correlate the PFT data and cyst features such as cyst number, size, and volume with the risk of spontaneous pneumothorax. These results will provide us the ability to do individual, patient-specific risk stratification for spontaneous pneumothorax in patients with BHD and PLCH.

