### 4.6. Data Elements

Data elements for this study include the following information about study participants:

- Contact information
- Demographics
- Age, gender, ethnicity
- Medical history
- Patient reported elements of diagnostic criteria and other clinical manifestations
- Surveillance information for associated clinical anomalies, such as renal tumors in BHD
- Evaluation of dyspnea, other pulmonary problems and need for supplemental oxygen

- Family history
- Smoking history
- Pneumothorax information (diagnosis, management, measures to prevent prevention such as pleurodesis, relationship with flights)
- Flight history
- Effect of pneumothoraces on attitudes towards undertaking air travel
- Pulmonary function tests
- CT scans

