#### **4.7. Schedule of Events**

September 2015: Distribute links and paper copies of the questionnaires

November 2015: Resend links and surveys to increase recruitment

January 2016: Data Analysis

April 2016: Manuscript submission

April 2017: Contact patients and start obtaining medical records

November 2017: Data Analysis

April 2018: Manuscript submission

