## **6.0 Statistical Considerations**

Data from all surveys will be pooled together. The rate of pneumothorax will be estimated as a percentage of the number of flights taken. We will compare other disease and patient characteristics to try to determine factors associated with an increased risk of in-flight pneumothorax. All analyses will be done by using SAS for Windows, version 9.4, Cary, NC.

NIH Approved 02-28-17

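### Objective 4 sets no time order between lung tests, pneumothorax and pleurodesis, so it can show an association but not the individual risk stratification stated in the Background

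*Protocol*

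**What the plan says.** Protocol Section 2.2 states Objective 4 as follows: "To determine the relationship between lung function, and radiographic cyst characteristics and the risk of spontaneous pneumothorax in patients with BHD and PLCH". The Lay Summary (1.2) gives the method only as obtaining test results "to correlate PFT data and cyst preponderance (size, number, volume etc.) with the risk for spontaneous pneumothorax". The Background (3.0) describes the source: "We will ask permission to obtain their medical records, specifically their pulmonary function tests (PFTs), and CT scan(s) of the chest". It then draws the conclusion at issue: "These results will provide us the ability to do individual, patient-specific risk stratification for spontaneous pneumothorax in patients with BHD and PLCH".

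The remaining pieces are spread over the protocol and SAP:

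- **Tests.** Section 4.7 has "April 2017: Contact patients and start obtaining medical records". This dates the retrieval of records. No dates are given for the tests, and no rule says which test is used when there are several.
- **Outcome.** Section 4.6 lists "Pneumothorax information (diagnosis, management, measures to prevent prevention such as pleurodesis, relationship with flights". Section 4.5 requires no follow-up after the survey. The outcome therefore appears to be the history reported in the survey. This is an inference, since no section says so directly.
- **Analysis.** Section 6.0 covers the per-flight rate ("The rate of pneumothorax will be estimated as a percentage of the number of flights taken") and factors for in-flight pneumothorax. Its approval stamp of 02-28-17 is later than Amendment 1 (02-23-17, Appendix 1), yet it has no text on Objective 4. The SAP is dated August 5, 2015, is titled for BHD only, and mentions neither PFT nor CT.

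**The concern.** A statement about an individual's future risk needs a measurement made before the event. Here a patient's only PFT or CT may have been taken after the pneumothorax, or after pleurodesis. If either changes lung function or the appearance of the cysts, affected patients will differ from unaffected ones because of the event. A correlation that pools all available tests would show that difference as a risk marker.

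At stake is how the result is used. Section 8.3 expects the study's answers to help inform clinical recommendations. An association presented as a personal risk tool would claim more than the data can carry.

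**Working it through.** The plan gives no event count, power or accuracy target for Objective 4, so there is no figure of its own to reproduce. The finding itself comes from reading the text. The arithmetic shows how far the bias could reach and what the repair costs.

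**1. Is a time order set anywhere?** Sections 1.2, 2.2, 3.0, 4.5 to 4.7 and 6.0, Appendix 1 and the SAP were read for a rule placing the test before the pneumothorax or pleurodesis. There is none.

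**2. Number affected.** Section 1.1 plans 200 PLCH patients. Section 3.0 says: "Approximately 15% of patients with PLCH develop a pneumothorax over their lifetime". Using that lifetime figure as a prevalence (an assumption), 200 × 0.15 = 30 affected and 170 unaffected. Section 3.0 also gives a recurrence rate of about 60%, so about 30 × 0.60 = 18 would have a recurrence. These counts assume that every participant is re-contacted and supplies records; at an assumed 50% they become 15 and 85. No absolute BHD rate is given.

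**3. Illustration of the bias.** Assume a marker with no true predictive value. A share f of affected patients is tested only after the event, and the event or its treatment shifts the marker by d SD. Both f and d are assumptions.

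- Mean difference: f·d
- Variance in affected patients: 1 + f(1−f)d²
- SE = √[(1 + f(1−f)d²)/n₁ + 1/n₀]
- P(p<0.05) = Φ(f·d/SE − 1.96) + Φ(−f·d/SE − 1.96), two-sided (the SAP gives 0.05 without saying one- or two-sided)
- Apparent AUC = (1−f)·0.5 + f·Φ(d/√2)

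Example with f = 1, d = 0.5: SE = √(1/30 + 1/170) = 0.198; 0.5/0.198 = 2.52; Φ(2.52 − 1.96) ≈ 0.71; AUC = Φ(0.354) = 0.64.

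| Affected v unaffected | Share post-event | d = 0.1 | d = 0.25 | d = 0.5 |
|---|---|---|---|---|
| 30 v 170 | all | 8% | 24% | 71% |
| 30 v 170 | half | 6% | 10% | 23% |
| 30 v 170 | none | 5% | 5% | 5% |
| 15 v 85 | all | 6% | 15% | 43% |
| 15 v 85 | half | 5% | 7% | 14% |

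Exact noncentral-t values for the first row are 7.9, 24.1 and 71.0%. With all tests post-event, the apparent AUC is 0.53, 0.57 and 0.64.

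**4. Cost of restricting to pre-event tests.** For a time-to-event analysis with 80% power, the detectable hazard ratio per SD is exp[(1.96 + 0.84)/√events].

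| Affected patients with a pre-event test | Detectable HR per SD |
|---|---|
| 30 | exp(2.80/5.48) = 1.67 |
| 20 | exp(2.80/4.47) = 1.87 |
| 15 | exp(2.80/3.87) = 2.06 |
| 8 | exp(2.80/2.83) = 2.69 |

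Simulated Cox models gave power of roughly 75% at 8 events, so the formula is slightly optimistic there.

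**The case against.** **The target is one sentence of rationale.** It stands in the Background, not in an objective or an analysis section, and the primary objective on flight-related risk is untouched. This stands, and it limits the weight of the point. A reader might infer that Objective 4 itself fails. The documents do not support that: its wording asks for a relationship, which a cross-sectional association can supply.

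**The dates may well be available.** A reader might infer that the time order cannot be recovered. That also goes too far. The SAP merges ipsilateral pneumothoraces reported in the same month, a rule that covers all pneumothoraces and cannot be applied without a month. This holds at least for BHD, the only disease in the SAP's title. Test records would normally carry dates. Pleurodesis dates are not mentioned, but the questionnaire is not in the documents, so their absence is not shown. The order is unspecified, not lost. Nor does the April 2017 entry show that the tests themselves were taken that late.

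**The size is assumed.** This stands too. The documents do not say that PFT or CT measures shift after a pneumothorax, nor how many tests are post-event. The 71% needs every affected patient to be tested only afterwards, together with a 0.5 SD shift. The illustration also assumes no predictive effect, whereas Section 3.0 says that cysts raise the risk in BHD. It shows that the bias is possible, not that it is present.

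**A repair could discard useful data.** Tests between a first and a later pneumothorax do precede the recurrence, so they deserve their own analysis. A fixed minimum such as 20 affected patients would be hard to justify when PLCH offers about 30 at most and about 15 at half participation.

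**Conclusion.** The point holds and should be acted on, as a matter of pre-specification and wording for a secondary objective. As written, the plan permits post-event tests to act as predictors and names no analysis for Objective 4. The result can be reported as an association. It does not give the ability to stratify individual patients, and it would not do so even with the time order fixed unless a model were also named and validated.

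The size of the bias is unknown. It is small if the measures shift little (5 to 8% false-positive results at 0.1 SD, against a nominal 5%) and substantial only under larger assumed shifts with many post-event tests. The conclusion does not depend on those assumptions. It does rest on the inference that the outcome is the survey history. If new pneumothoraces were collected after the tests, that part could be time-ordered, but no section describes such collection.

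**What to change.** Add an Objective 4 analysis to Section 6.0 and to an updated SAP that covers both diseases:

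1. **Dates.** Take the date of each PFT and CT from the records and the pneumothorax month from the survey. Obtain pleurodesis dates, and any missing pneumothorax dates, at the planned re-contact.
2. **Predictive analysis.** Base any predictive statement on tests dated before the first pneumothorax and before any pleurodesis, and state in advance which test is used if several qualify. Follow each patient from the test date to first pneumothorax or to the last date on which status is known, which is the survey date unless status is updated. Treat a test from the same month as the event, with unknown order, as post-event.
3. **Other tests.** Report the all-tests correlation as a cross-sectional association. Analyse tests between a first and a later pneumothorax separately for recurrence, taking account of intervening pleurodesis.
4. **Claim.** Unless a pre-event analysis proves feasible and is at least internally validated (discrimination and calibration by resampling), reword the Background sentence to an exploratory cross-sectional association. No fixed minimum count is needed.

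**Cost.** Protocol and SAP text, date fields and a few date questions at a contact that is already planned. The main loss is precision, because patients without a pre-event test leave the predictive analysis. Asking about pneumothoraces since the survey would lengthen follow-up but is optional. It would be an added procedure, needing its own review, since Section 4.5 requires no follow-up. If none of this is wanted, rewording the one sentence is enough.

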## 4.0 Study Design and Methods

### 4.1. Overview

Online surveys will be created in REDCap, a password protected data management software, and the links distributed to all patients via email. In case of lack of Internet access or personal preference, paper copies of the surveys will be mailed out to the patients along with a prepaid, addressed return envelope.

### 4.2. Inclusion Criteria

- Adult, age 18 or older
- English literate
- Signed, dated informed consent; either given electronically or via paper form;
- Diagnosis of BHD, or PLCH as defined by accepted clinical, histopathological and/or genetic criteria
  - *For BHD, diagnosis would include the presence of fibrofolliculomas/trichodiscomas on skin biopsy, or the presence of pathogenic FLCN mutations.*
  - *For PLCH, diagnosis would include characteristic radiographic findings and tissue biopsy consistent with PLCH (presence of CD1a positive Langerhans cells or stellate fibrosis in late stages).*

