## 1.0 Overview

### 1.1. Protocol Synopsis

Protocol Number:	5714
Protocol Title:	Assessment of Safety of Air Travel in Patients with Diffuse Cystic Lung Disease
Study Chair:	[name]
Statistician:	[name]
Consortium:	Rare Lung Diseases
Participating Sites:	University of Cincinnati
Activation Date:	December 4, 2015
Sample Size:	300 subjects - 100 with Birt-Hogg-Dubé Syndrome (BHD), 200 with Pulmonary Langerhans Cell Histiocytosis (PLCH)
Target Enrollment Period:	September 2015 – September 2016
Study Design:	This is a questionnaire-based study of patients with diffuse cystic lung diseases (DCLDs) to gather information relevant to safety of air travel, especially pertaining to the risk of pneumothorax associated with air travel. In addition, this study will be used to further characterize clinical aspects of disease and establish a contact registry for patients.
Primary Study Objective(s):	To define the risk of pneumothorax associated with air travel in patients with DCLD.
Secondary Study Objective(s):	

• To establish a contact registry for patients with BHD and PLCH

• To define the clinical phenotype of each DCLD in their respective cohort of patients

• To define current screening practices for surveillance of disease-specific anomalies (i.e. renal tumors in BHD)

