## **2.0 Specific Aims (Hypothesis and Objectives)**

### **2.1. Hypothesis**

The hypothesis to be tested is that air travel is safe in patients with diffuse cystic lung diseases, and there is no increased risk of pneumothorax in this disease population related to air travel.

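### The protocol pools BHD and PLCH into one per-flight pneumothorax rate, so neither disease is assured its own figure; report the rate by disease, with a known-cyst BHD rate as an optional extra

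*Protocol*

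**What the plan says.** **Objective.** Protocol 2.2 sets the first objective as "To define the risk of pneumothorax related to air travel in patients with BHD and PLCH". The Synopsis (1.1) has "To define the risk of pneumothorax associated with air travel in patients with DCLD", and the hypothesis (2.1) is that "air travel is safe in patients with diffuse cystic lung diseases".

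**Purpose.** Section 3.0 notes that "disease specific data for safety of air travel in BHD are lacking" and states: "Having specific information about safety of air travel in BHD and PLCH will help these patients make informed decisions about air travel".

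**Analysis.** Section 6.0 and the statistical row of the Synopsis merge the data from all surveys and express pneumothoraces as a percentage of flights. Neither mentions a rate by disease. The SAP, dated August 2015, gives the same single rate. Its title names BHD only, and its text mentions neither PLCH nor pooling. Both documents add a general comparison of patient and disease features, without naming diagnosis or cyst status.

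**Entry and cysts.** Section 4.2 reads: "For BHD, diagnosis would include the presence of fibrofolliculomas/trichodiscomas on skin biopsy, or the presence of pathogenic FLCN mutations". PLCH entry, by contrast, requires characteristic imaging. The only exclusion (4.3) is inability to consent. Section 3.0 says: "Pulmonary cysts are seen in 80-100% of patients with BHD". The amendment (2.2 objective 4, and 3.0) relates CT cyst features to spontaneous pneumothorax, not to the per-flight rate.

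**The concern.** The study exists because patients with BHD and with PLCH are advised by extrapolation from other diseases. One rate across both repeats that problem on a smaller scale: each group is told a figure weighted by the other's flights. The two diseases differ in cause and in pneumothorax history, and nothing in the documents suggests that their per-flight risks are equal. Change the recruitment mix and the pooled rate changes, even if neither disease's risk does. The protocol and the SAP also leave it unclear which population the primary rate describes.

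Cysts raise a narrower question. The feared mechanism is the "risk of cyst expansion with decreasing atmospheric pressure, which could lead to cyst rupture causing a pneumothorax", but a BHD participant may have no cysts. No planned figure describes the BHD patients to whom that mechanism applies.

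**Working it through.** **Inputs from the documents.** Planned sample 100 BHD + 200 PLCH = 300, which matches the Synopsis total. Cysts in 80-100% of BHD, so 0-20% are cyst-free. The documents give no per-flight rate, flight count, expected event count or precision target, so the ratios below are assumptions shown over a range.

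**Step 1: BHD rate against the pooled rate.** Let R be the BHD per-flight rate divided by the PLCH rate, and w the BHD share of all flights. Then BHD/pooled = R / (wR + 1 − w). With 100:200 and equal flying, w = 1/3 and this becomes 3R/(R + 2). The PLCH ratio is 3/(R + 2).

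| R (assumed) | BHD / pooled | PLCH / pooled |
|---|---|---|
| 0.5 | 1.5/2.5 = 0.60 | 3/2.5 = 1.20 |
| 1 | 1.00 | 1.00 |
| 2 | 6/4 = 1.50 | 3/4 = 0.75 |

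The answer also moves with the flight mix. If BHD participants fly twice as much, w = 200/400 = 0.5, and the BHD ratio is 0.5/0.75 = 0.67 at R = 0.5 and 2/1.5 = 1.33 at R = 2.

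**Step 2: the price in precision.** If the two rates and flying are equal, relative interval width grows roughly with the square root of the flights lost: √(300/100) = 1.73 times for BHD and √(300/200) = 1.22 times for PLCH.

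**Step 3: cyst-free BHD participants, within BHD only.** Let p be the cyst-free share, k their flights per person relative to cystic participants, and r their per-flight risk relative to cystic participants. With q = pk/(pk + 1 − p), cystic-BHD rate / all-BHD rate = 1/(1 − q(1 − r)).

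| p | k | r | Factor |
|---|---|---|---|
| 0 | any | any | 1.00 |
| 0.10 | 1 | 0 | 1/0.90 = 1.11 |
| 0.20 | 1 | 0 | 1/0.80 = 1.25 |
| 0.20 | 1 | 0.25 | 1/0.85 = 1.18 |
| 0.20 | 1 | 0.5 | 1/0.90 = 1.11 |
| 0.20 | 0.5 | 0 | 1/0.889 = 1.13 |
| 0.20 | 2 | 0 | 1/0.667 = 1.50 |

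The values of k and r are assumed.

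**Step 4: cystic-BHD rate against the pooled rate.** Take 80 cystic BHD, 20 cyst-free BHD without events, 200 PLCH and equal flying, and let s be the PLCH rate divided by the cystic-BHD rate. The ratio is 300/(80 + 200s): 300/180 = 1.67 at s = 0.5, 300/300 = 1.00 at s = 1.1, and 300/480 = 0.63 at s = 2. The sign depends on s, which is unknown.

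**Step 5: sampling error.** With an assumed 4 events, the exact Poisson 95% interval runs from 0.27 to 2.56 times the estimate. About 77 events are needed before the upper limit falls to 1.25 times the estimate.

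**Step 6: how a known-cyst rate can err.** Assume 1,000 BHD flights, 200 of them by cyst-free people, and 4 events, all in cystic people. The all-BHD rate is 4/1000 = 0.40% and the true cystic rate is 4/800 = 0.50%. If 10% of cystic flights, all event-free, are dropped as cyst status unknown, the known-cyst rate is 4/720 = 0.56%. If half the cyst-free flights are misreported as cystic, it is 4/900 = 0.44%.

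**The case against.** **Separate reporting may already be intended.** The SAP is titled for BHD and does not pool; section 3.0 sends out the BHD questionnaire first and the PLCH survey later; a secondary objective describes phenotype by cohort. The pooling sentence might even mean only that online and paper surveys are merged. This stands in part: it is unfair to say that both documents commit to a cross-disease rate. But section 6.0 places the pooling statement directly before a single rate with no split, and nothing reconciles it with the SAP. On either reading, the text does not commit to a rate for each disease.

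**The objective as worded is met without a cyst restriction.** Objective 1 concerns patients with BHD and PLCH, and the Synopsis appears to use DCLD as a label for those two diseases. This stands. The unrestricted rate is valid, and a cyst-restricted rate is an optional subgroup.

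**The cyst-free share may be well under 20%.** Section 4.4 recruits partly through rare-lung-disease clinics, which supports this. The same section also recruits through the BHD Foundation and a BHD symposium, so the share is unknown.

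**The general comparison and the CT work could cover cysts.** They could inform the question. However, the comparison does not name cyst status or promise an absolute rate, and the CT work has a different outcome and covers only re-contacted participants who agree.

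**A stronger inference to avoid.** A reader might infer that, because cyst-free BHD patients are admitted, the pooled rate understates risk in cystic BHD by some modest factor. The documents do not support this. Against the pooled rate the direction depends on the PLCH per-flight rate (step 4), which they do not give.

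**Conclusion.** The point holds for reporting by disease. Over an assumed BHD:PLCH rate ratio of 0.5 to 2, with the planned split and equal flying, the BHD rate is 0.60 to 1.50 times the pooled rate. The direction is unknown, and if the two rates are equal there is no distortion. The pooled rate is a valid description of the mixed sample; it does not supply the disease-specific information that the Background asks for.

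The cyst point is secondary. Within BHD, the all-BHD rate may be too low for cystic patients by a factor of 1.00 to 1.25 at equal flying with no events in cyst-free people, and by up to 1.50 if cyst-free people fly twice as much. The 1.25 is the extreme of its range, not an expected value. With few events, a shift of that size is small against sampling error. It does not undermine the all-BHD rate, and it says nothing about the direction of error in the pooled rate. The change is worth making because it is cheap and serves the study's stated purpose.

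**What to change.** 1. Amend section 6.0, the matching Synopsis row and the SAP so that the primary per-flight rate is reported separately for BHD and PLCH, each with an exact confidence interval. Keep the pooled rate as secondary. Have the SAP state that it covers both diseases.
2. Word each conclusion for the population whose rate supports it.
3. Optional: if the patient-reported diagnostic and clinical items in section 4.6 captured lung cysts, add a descriptive BHD rate limited to participants with known cysts, restricting events and flights alike. Use CT as a check where obtained. State that this rate can err high, because a pneumothorax may prompt imaging, or low, if cysts are misreported. It supplements the all-BHD rate and does not replace it.

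**Cost.** Items 1 and 2 need wording and a little analysis of data already collected, with no new survey and no change to eligibility. Intervals for each disease will be wider than the pooled one, by the factors in step 2. Item 3 depends on a questionnaire that is not shown. Its interval would be about √(1/0.80) = 1.12 times as wide relative to the rate if 20% of BHD flights drop out and events fall in proportion, or √(1/0.64) = 1.25 times if a further 20% of the remainder have unknown cyst status (assumed).
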